9.3. Analysis of Outcome Measures

A pre-post design will be used to determine whether the use of ITGs lead to a significant improvement in the psychosocial wellbeing of people with facial palsy and or their friends and relatives, as measured by the Hospital Anxiety and Depression Scale, Face-Q – Social function (people with facial palsy only), Face-Q – Psychological function (people with facial palsy only), Face-Q – Appearance-related psychosocial distress (people with facial palsy only) and the Facial Disability Index (people with facial palsy only). This change will be measured for each individual ITG, using paired-samples t-tests. The Facial Disability Index can also be used to control for improvement in facial palsy symptoms, when assessing the impact of ITGs on scores on measures of psychological wellbeing. In the instance of a significant change in facial palsy symptoms being observed, separate ANCOVAs will be used, with Facial Disability Index score being used as a covariate and scores on individual measures of psychosocial wellbeing serving as within-subjects factors.

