1. SYNOPSIS

Study Title	A pilot study evaluating the effectiveness of information and therapy guides for improving the psychosocial wellbeing of people with facial palsy.	
Study Design	Feasibility/pilot study	
Study Participants	Adults with a diagnosis of facial palsy and/or their friends and relatives	
Planned Sample Size	140 participants	
Planned Study Period	July 2019 – May 2021	
	Objectives	Outcome Measures
Primary	To evaluate the effectiveness of Information and Therapy guides (ITG) at improving the psychosocial wellbeing of people with a diagnosis of facial palsy	Hospital Anxiety and Depression Scale Face-Q – Social function Face-Q – Psychological function Face-Q – Appearance-related psychosocial distress Facial Disability Index
Secondary	To evaluate the effectiveness of Information and Therapy guides at improving the psychosocial welling of family and friends of people with a diagnosis of facial palsy	Hospital Anxiety and Depression Scale Adult Carer Quality of Life Questionnaire
Tertiary	To evaluate the acceptability and usability of Information and Therapy guides for people with facial palsy and/or their family and friends	Patient satisfaction questionnaire

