5. STUDY DESIGN

Given that this study represents an initial pilot of the use of ITGs for people with facial palsy (and/or their friends and relatives), all eligible participants will receive the intervention (i.e. there will be no control group). As a result, this study will have a repeated-measures design.

Eligible participants will be recruited by one of two means:

- 1) Face-to-face of recruitment of OUH NHS patients during clinics at the Oxford Facial Palsy Service
- 2) Recruitment of people with facial palsy, not under the care of the Oxford Facial Palsy Service, through relevant web and social media pages (e.g. the Facial Palsy UK Facebook page)

Potential participants who have expressed an interest in the study will be provided with an information sheet and if still interested they will be invited to provide written consent (via an online consent form; Survey Hero). They will then be screened for eligibility using an online screening questionnaire (also Survey Hero). Participants recruited in Oxford Facial Palsy Service clinics will complete the screening questionnaire on the researcher's laptop during clinic or online at a later date if they wish to have more time to consider their participation in the study. Participants recruited on social media will be emailed a link to the screening questionnaire. Participants will have provided written consent for their email address to be shared with the research team.

Eligible participants will then be invited to complete baseline questionnaires:

People with facial palsy: Hospital Anxiety and Depression Scale; FACE-Q Satisfaction with appearance; FACE-Q Psychological function; FACE-Q Social function and Facial Disability Index.

Friends, relatives or partners: Hospital Anxiety and Depression Scale and Adult Carer Quality of Life Questionnaire.

Like the consent forms and screening questionnaires, baseline questionnaires will be completed online via Survey Hero.

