FACE-Q Social functioning (18): Like the FACE-Q psychological function scale, participants are provided with a series of positively worded statements. In this scale there are 9 statements and they pertain to measuring social functioning. Just as with the psychological function scale, the social functioning scale has a Cronbach alpha of .96 and has been shown to have good convergent and discriminant construct validity.

Facial Disability Index (19): A 10-item self-report measure of physical and social function in people with facial palsy. Both the physical (=.88) and social (=.83) subscales have been shown to have good internal consistency and construct validity (19). Each scale is scored out of 100 (100 = high function).

This measure of facial function will allow the researchers to control for improvement or decline in facial palsy symptoms when assessing the impact of the ITG's on psychological wellbeing.

Note: the friends/relatives of participants with facial palsy are not required to complete questionnaires, unless they themselves are actively participating in the study (i.e. are trialling the family, friend or partner ITG)

Secondary Objectives

To evaluate the effectiveness of Information and Therapy guides at improving the psychosocial welling of friends and relatives of people with a diagnosis of facial palsy

This will be assessed by the change in friend's/relative's self-report questionnaires before and after a four-to-six week intervention using the information and therapy guide: Facial palsy: Advice for friends, relatives and partners of people with facial palsy.

The outcome measures used will be the **Hospital Anxiety and Depression Scale** (described above), along with the **Adult Carer Quality of Life Questionnaire** (20). This is a 40-item self-report scale that measures the overall quality of life for adult carers. Subscale scores include: support for caring; caring choice; caring stress; money matters; personal growth; sense of value; ability to care and carer satisfaction. Scores fall on a 0-120 scale, with higher scores indicating better quality of life.

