9. STATISTICS AND ANALYSIS

9.1. Description of Statistical Methods

This study will follow a pre-post design and as such will use paired t-tests to observe whether a statistically significant change has occurred on each of the outcome measures, for each ITG. Descriptive statistics will also be provided (e.g. mean scores on each outcome measure at baseline).

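### The Facial Disability Index is both a primary wellbeing outcome and the control for facial recovery, with no split by subscale, so a significant rise on it has two opposite readings

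*Combined protocol and SAP*

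**What the plan says.** **As an outcome.** The synopsis (section 1) and the objectives table (section 4) list the FDI under the primary objective, which is improved psychosocial wellbeing in people with facial palsy; the synopsis entry ends "Appearance-related psychosocial distress Facial Disability Index". Section 9.3 names it again among the measures that will show whether the guides improve wellbeing. Section 9.1 says the study "will use paired t-tests to observe whether a statistically significant change has occurred on each of the outcome measures, for each ITG".

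**As a control.** Section 7.4 says of the same index: "This measure of facial function will allow the researchers to control for improvement or decline in facial palsy symptoms". Section 9.3 repeats this role: "The Facial Disability Index can also be used to control for improvement in facial palsy symptoms". It then makes the adjustment conditional: "In the instance of a significant change in facial palsy symptoms being observed, separate ANCOVAs will be used", with the FDI score as covariate.

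**Content.** Section 7.4 describes the FDI as "A 10-item self-report measure of physical and social function in people with facial palsy", with a physical and a social subscale, each scored out of 100. Sections 1, 4 and 9.3 name only the index as a whole.

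**Design.** Section 5 states that "there will be no control group".

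**The concern.** The two roles pull in opposite directions. As an outcome, a rise in the FDI is evidence for the guide. As a control, the same rise is facial recovery, to be removed before the guide is judged. The plan does not say which reading applies, or which subscale carries it.

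The guides draw on cognitive behavioural therapy, social skills training and acceptance and commitment therapy (section 8), and the protocol gives no route by which they would restore facial function. Recovery can occur without them: section 3 says that up to 70% of people with Bell's palsy, by far the commonest cause, recover fully. The early-stages guide is offered to people who report onset in the last six months (section 7.2).

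Two errors are possible. Recovery of the face could be reported as a gain on a primary wellbeing measure. Conversely, a gain in social function, which a guide might plausibly produce, could be treated as symptom recovery and adjusted away from the other measures.

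**Working it through.** **1. Roles side by side**

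| Place | Role given to the FDI | Subscale named for that role |
|---|---|---|
| Sections 1 and 4 | Outcome of the primary objective | None |
| Section 7.4 | Control for change in symptoms | None (both subscales are described) |
| Section 9.3, outcome list | Measure of improved wellbeing, paired t-test per guide | None |
| Section 9.3, adjustment | Covariate if symptoms change significantly | None |

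The conflict is established by the text alone. The figures below only indicate its possible size.

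**2. Sample size.** Section 9.2 gives 20 users for each of six guides plus 20 friends and family: 6 × 20 + 20 = 140, which matches the stated total. So n = 20 per guide. No power analysis was done.

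**3. Chance that recovery alone gives a significant FDI physical improvement.** The documents give no significance level, recovery share, FDI change or SD. Assumptions:
- the guide has no effect;
- a share p of users gains g points on the 0–100 physical subscale, and the rest do not change on average;
- other change has SD s, between 10 and 20 points;
- the test is a two-sided 5% paired t-test (critical t on 19 df = 2.093).

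Formulas: mean change = p·g; SD of change = √(s² + p(1−p)g²); noncentrality = √20 × mean / SD; chance = upper tail of the noncentral t beyond 2.093.

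Worked example, p = 0.25, g = 20, s = 10: mean = 5; SD = √(100 + 75) = 13.23; noncentrality = 4.472 × 5 / 13.23 = 1.69; chance = 36%.

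| Share recovering, gain | Mean change | s = 10 | s = 15 | s = 20 |
|---|---|---|---|---|
| 5%, 10 points | 0.5 | 4% | 3% | 3% |
| 10%, 10 points | 1.0 | 6% | 5% | 4% |
| 25%, 10 points | 2.5 | 16% | 10% | 7% |
| 25%, 20 points | 5.0 | 36% | 23% | 16% |
| 50%, 20 points | 10.0 | 85% | 65% | 48% |

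The nominal rate in this direction is 2.5%. The formula treats change as normal although recovered and unrecovered users form a mixture. Simulating the mixture at s = 10 (200,000 runs) gave 16%, 35% and 85% for the last three rows, so the approximation is adequate.

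**4. What the planned ANCOVA protects.** A second simulation (40,000 runs, n = 20, no guide effect) used a standardised FDI change d of 0.2 to 0.8 and a correlation of 0.3 or 0.5 between FDI change and change on another wellbeing measure. The FDI's own test was taken as the trigger, and the adjustment was modelled as the mean wellbeing change at zero FDI change. False improvement on the other measure was:
- unadjusted: 4% to 39%;
- under the conditional rule: about 3% to 5%;
- always adjusted: about 2.5%.

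The FDI itself showed significant improvement in about 14% of runs at d = 0.2, 25% at 0.3, 57% at 0.5 and 92% at 0.8. No adjustment applies to that result.

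**The case against.** The strongest reply is that the planners foresaw recovery. Section 7.4 calls the FDI a measure of facial function, and section 9.3 treats significant symptom change as the reason to adjust. A reader of the plan would therefore already doubt that an FDI rise is a guide effect. The adjustment also does useful work for HADS and FACE-Q, as step 4 shows. This stands, with the reservation that section 9.3 words the control as something that can be used. It does not help the FDI result.

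A second reply is that the FDI partly belongs in the outcome list, since it covers social function. That also stands, and it is why the remedy is to divide the index rather than drop it. Section 9.3 never says that the physical score is tested separately; it leaves the scoring of the index open.

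Third, the recovery premise has limits. The 70% figure is an upper bound for Bell's palsy and has no time frame, whereas follow-up is four to six weeks plus a two-week response window (section 5). Section 3 adds that people who recover spontaneously are unlikely to reach facial palsy services, though this bears on clinic recruitment rather than recruitment through the charity. Only the early-stages statement specifies recent onset. Where few users recover, the excess over 2.5% is small.

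A reader might infer that facial recovery could make a guide succeed overall, or that every primary measure is equally exposed. The documents support neither: there is no success rule across the primary measures, and the other measures have a planned adjustment.

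Finally, an uncontrolled pilot leaves every measure open to natural change. That is so, but the FDI differs in being the plan's own designated marker of that change.

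**Conclusion.** The concern holds for one listed primary measure. As written, a significant FDI rise can be reported as improved wellbeing and also taken as evidence that the palsy changed, and neither the design nor the ANCOVA can separate these for the FDI itself.

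The size is uncertain because every input except n = 20 is assumed. Over SDs of 10 to 20, the chance of a significant physical improvement with an inert guide is about 3–6% if 5–10% of users gain 10 points, 7–16% if 25% gain 10, 16–36% if 25% gain 20, and 48–85% if half gain 20. The higher figures are relevant mainly to the early-stages guide and need substantial recovery within weeks. The change is worth making because effectiveness is the stated primary objective and the conflict is cheap to remove; the conclusion does not depend on any one percentage.

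**What to change.** In sections 1, 4, 7.4 and 9.3, replace the undivided index with its two existing subscales:
- name the FDI social subscale as the effectiveness outcome, and do not use it as a marker of recovery;
- name the FDI physical subscale as the marker of disease course, and as the only FDI score used for the symptom-change trigger and the ANCOVA covariate;
- state that change in the physical subscale will be reported descriptively for each guide and not as evidence of effectiveness.

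The cost is wording in four sections and one fewer effectiveness outcome per guide. No new data or participants are needed.

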10. DATA MANAGEMENT

10.1. Access to Data

Direct access will be granted to authorised representatives from the Sponsor and host institution for monitoring and/or audit of the study to ensure compliance with regulations.

10.2. Data Recording and Record Keeping

None of the study documents besides the identification log (and consent forms) will contain any identifiable data.

Participants are assigned a study ID and this will be used on all online questionnaires, study documents and the database which will contain no identifiable data, they will only be identifiable on the ID log linking the ID number and their personal information.

The log of study IDs will be kept electronically and separately from participant data and will only be accessible by members of the research team.

Electronic copies of consent forms will be kept in password protected file, separate to completed questionnaires, which will be kept securely and separately in a password protected file.

Hard copies of consent forms will be kept in the Study Master File, separate to completed questionnaires, which will be kept securely and separately to the Study Master File. These will be in a locked filing cabinet in the Russell Cairns Unit, Level 3 West Wing, John Radcliffe Hospital.

Questionnaire data will be transferred to an excel sheet and SPSS datasheet.

These databases, and ID log, will be kept separately on a password protected database/spreadsheet stored on NHS servers.

The database will be tested at regular intervals to ensure accuracy. This will be done by the lead researcher selecting one participant at random, to ensure that the data has been entered accurately.

The Study Master File and anonymised research data will be kept for 5 years.

Contact details for parents who'd like to receive a copy of the results will be stored for 12 months and kept securely and separately to any anonymised research data.

Survey Hero is GDPR compliant.

11. QUALITY ASSURANCE PROCEDURES

The study may be monitored, or audited in accordance with the current approved protocol, GCP, relevant regulations and standard operating procedures.

12. ETHICAL AND REGULATORY CONSIDERATIONS

12.1. Declaration of Helsinki

The Investigator will ensure that this study is conducted in accordance with the principles of the Declaration of Helsinki.

12.2. Guidelines for Good Clinical Practice

The Investigator will ensure that this study is conducted in accordance with relevant regulations and with Good Clinical Practice.

12.3. Approvals

The protocol, informed consent form, participant information sheet and any proposed advertising material will be submitted to an appropriate Research Ethics Committee (REC), and HRA for written approval.

The Investigator will submit and, where necessary, obtain approval from the above parties for all substantial amendments to the original approved documents.

12.4. Reporting

The CI shall submit once a year throughout the study, or on request, an Annual Progress report to the REC Committee, HRA (where required) host organisation and Sponsor. In addition, an End of Study notification and final report will be submitted to the same parties.

12.5. Participant Confidentiality

The study staff will ensure that the participants' anonymity is maintained. The participants will be identified only by a participant ID number on all study documents and any electronic database. All documents will be stored securely and only accessible by study staff and authorised personnel. The study will comply with the Data Protection Act, which requires data to be anonymised as soon as it is practical to do so. No identifiable data will be published.

12.6. Expenses and Benefits

Since data collection will take place at routine clinic appointment or via email/web-based survey, travel expenses will not be reimbursed.

12.7. Other Ethical Considerations

The questionnaires used in this study include topics that may be sensitive for certain participants. For example, certain questions ask about the participant's mood and anxiety. In particular, the Hospital Anxiety and Depression Scale will indicate whether participants are experiencing clinically significant anxiety and/or depression. If participants report clinically significant anxiety and/or depression, then the lead researcher will contact the participant on the telephone (or talk to the participant if meeting face-to-face in clinic) to inform them of that their score is indicative of elevated levels of anxiety and/or depression and that we recommend that they contact their GP to discuss this further. We will also provide emergency/out of hours information (if it is out of hours and your GP surgery is closed, dial 111 if they wish to speak with a GP. If it is an emergency situation call 999.)

The consent form contains information for participants informing them that the research team will not be providing psychological treatment for participants, beyond the use of ITGs, and as such participants should contact their GP, rather than the research team, if they are concerned about their psychological wellbeing.

13. FINANCE AND INSURANCE

13.1. Funding

This project is funded by the VTCT foundation. The VTCT Foundation awarded £61,383.88 for use over a 30 month period. This grant covers the salary for the lead researcher (0.4 wte), as well as research costs, design and printing costs and conference/travel costs.

13.2. Insurance

NHS bodies are legally liable for the negligent acts and omissions of their employees. If you are harmed whilst taking part in a clinical research study as a result of negligence on the part of a member of the study team this liability cover would apply.

Non-negligent harm is not covered by the NHS indemnity scheme. The Oxford University Hospitals NHS Foundation Trust, therefore, cannot agree in advance to pay compensation in these circumstances.

In exceptional circumstances an ex-gratia payment may be offered.

14. PUBLICATION POLICY

The Investigators will be involved in reviewing drafts of the manuscripts, abstracts, press releases and any other publications arising from the study. Authors will acknowledge that the study was funded by the VTCT Foundation. Authorship will be determined in accordance with the ICMJE guidelines and other contributors will be acknowledged.

16. APPENDIX A: AMENDMENT HISTORY

Amendment No.	Protocol Version No.	Date issued	Author(s) of changes	Details of Changes made

List details of all protocol amendments here whenever a new version of the protocol is produced. This is not necessary prior to initial REC submission.

APPENDIX B – FLOW CHART
